10.5 End of Study Visit

Patients will have their EOS 4 weeks (\pm 2 days) following:

- The last administration of MOR00208 in Cycle 2 if the response after 2 cycles was not at least SD
- The visit where a relapse (or disease progression) was diagnosed or decision to stop treatment was made in patients qualifying for Cycle 3 of MOR00208

If patient terminates the study early (ie, before end of Cycle 2), the EOS will be performed on the day of termination.

The assessments that will be performed at the EOS include the following:

- Assessment of AEs and concomitant medication
- Assessment of body weight
- Physical examination including palpable tumor assessment, general appearance, skin, head, eyes, ears, nose, throat, lungs, breasts and axillae (if applicable including bi-dimensional measurement of cervical, supraclavicular, axillary and inguinal lymph nodes), cardiovascular system, back and spine, abdomen (if applicable including spleen size below costal margin), extremities, infusion site, lymph nodes, and neurological examinations
- ECOG performance status
- Vital signs (pulse, blood pressure, temperature, respiratory rate)
- Response assessment includes:
 - Assessment by physical examination
- Laboratory assessments from blood sampling:
 - Haematology including CBC with differential and platelet count and serum chemistry
 - Coagulation

- B-, T- and NK cell flow cytometry
- Serum immunoglobulin levels
- β -HCG pregnancy test for women of childbearing potential
- Laboratory assessments from urine sampling: Urinalysis
- ECG

Patients who were positive for anti-HBc at screening should be followed up for potential HBV reactivation as per local practice (refer to [Section 9.5.2](#)).

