9.11.2 Study Drug Discontinuation

Study drug must be discontinued for a given patient if the investigator determines that continuing it would result in a significant safety risk for the patient.

Patients who discontinue study before completing the second cycle and response assessment should be scheduled for a visit as soon as possible, at which time all of the assessments listed for the End of Study visit should be performed. At a minimum, all patients who discontinue study treatment, including those who refuse to return for a final visit, will be contacted for safety evaluations during the first 4 weeks following the last dose of study drug.

Patients who discontinue study drug should be considered withdrawn from the study after the final visit assessments are performed or when it becomes clear that the patient will not return for these assessments. The last day of study drug administration should be entered into the eCRF and the reason for discontinuing study drug should be given. Patients lost to follow-up should be recorded as such in the eCRF. Treatment after study drug discontinuation is at the discretion of the investigator.

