10 VISIT SCHEDULE AND ASSESSMENTS

[Table 2](#) lists all of the assessments, and indicates with an "X" the visits at which these assessments are performed. All data obtained from these assessments must be supported in the patient's source documentation.

Table 2 Schedule of Assessments

Evaluation or Procedure	Screening	Cycle 1 (28 days)					Cycle 2 (28 days)					Cycle 3 (if response is at least SD) (2 weeks ± 1 day after Cycle 2 Day 22)					Follow-up		Maintenance Treatment Visits beyond Follow-up Visit 12 ²⁰	EOS Visit	
		-21 to -1	Day 1	Day 2	8 ± 1 day	15 ± 1 day	22 ± 1 day	1 ± 1 day	8 ± 1 day	15 ± 1 day	22 ± 1 day	28 ± 4 days	1 ± 1 day	8 ± 1 day	15 ± 1 day	22 ± 1 day	28 ± 4 days	1 st Follow-up + 4 weeks ± 2 days			Follow-up Visits 2 - 12 ¹
Informed consent	X																				
Inclusion/exclusion criteria	X	X ²																			
Demography	X																				
Medical history (incl. prior NHL treatments)	X																				
Staging	X																				
ECOG	X	X			X		X		X				X		X			X	X		X
Determination of CD19 on tumor cells (bone marrow)	X																				
Determination of CD19 on tumor cells (tumor biopsy/aspirate) ³	X																				
Study drug administration		X		X	X	X	X	X	X	X		X	X	X	X					X ²⁰	
Premedication		X		X	X	X ⁴	X ⁴	X ⁴	X ⁴	X ⁴		X ⁴	X ⁴	X ⁴	X ⁴						
“Emergency laboratory”		X ¹⁹		X ¹⁹	X ¹⁹	X ¹⁹	X ¹⁹	X ¹⁹	X ¹⁹	X ¹⁹		X ¹⁹	X ¹⁹	X ¹⁹	X ¹⁹						
Haematology	X	X ²	X	X ²	X ²	X ²	X ²	X ²	X ²	X ²	X	X ²	X ²	X ²	X ²	X	X	X	X	X	X
Serum chemistry	X	X ²	X	X ²	X ²	X ²	X ²	X ²	X ²	X ²	X	X ²	X ²	X ²	X ²	X	X	X	X	X	X
Coagulation	X	X ²					X ²					X ²					X	X	X		X
Pharmacokinetics		X ⁵		X ⁶	X ⁶	X ⁶		X ⁶		X ⁶	X		X ⁶		X ⁶	X	X	X ⁷			
Urinalysis	X	X ²					X ²					X ²					X	X			X
β-HCG pregnancy test (WOCBP)	X																X ²²	X ²²			X
Urine pregnancy test (WOCBP)		X ²					X ²					X ²					X ²²	X ²²	X		
Serology (Hepatitis B and C)	X					X ²¹					X ²¹					X ²¹	X ²¹	X ²¹	X ²¹		
B-, T- and NK cell flow cytometry		X ²		X ²	X ²	X ²		X ²		X	X ²		X ²		X						X
CD16 expression on NK cells	X						X ²					X ²					X	X ¹⁸			
Anti-MOR00208 antibodies		X ²					X ²					X ²									
FcγR polymorphism (mucosal cheek swab)		X ²																			

Table 2 Schedule of Assessments

Evaluation or Procedure	Screening	Cycle 1 (28 days)					Cycle 2 (28 days)					Cycle 3 (if response is at least SD) (2 weeks ± 1 day after Cycle 2 Day 22)					Follow-up		Maintenance Treatment Visits beyond Follow-up Visit 12 ²⁰	EOS Visit + 4 weeks ± 2 days	

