10.8.1 Adverse Events

An adverse event (AE) is defined as any untoward medical occurrence in a patient or clinical subject administered a medicinal product, which does not necessarily have a causal relationship to this treatment.

An AE can therefore be any unfavourable and unintended sign (including an abnormal laboratory finding), symptom, or disease temporally associated with the use of a study drug, whether or not it is considered related to that study drug.

Temporally associated means after signing the informed consent form until 30 days after last administration of the study drug.

For screening failure patients only SAEs will be recorded in the eCRF.

AEs include any clinically significant deterioration of a patient's medical status after the signing of the informed consent form. Also an increase in frequency or intensity of a preexisting episodic event or conditions and events resulting from protocol mandated procedure (eg, invasive procedures) fall under the definition of AE. In addition, overdoses (defined as exceeding planned dose by more than 10%) should be recorded as AEs.

As far as possible, each AE should be evaluated to determine the following:

- Relationship to study drug (suspected/not suspected)
- Duration (start and end date or if continuing at end of study)
- Intensity: The intensity of all AEs will be graded as mild, moderate, or severe using the following definitions:
 - Mild: Tolerable
 - Moderate: Interferes with normal activity
 - Severe: Incapacitating (causes inability to perform usual activity or work)

- Toxicity grade: The toxicity grade of AEs will be graded according to the NCI-CTC (CTCAE version 4.0 of May 28, 2009) using the following definitions:
 - Grade 1: Mild; asymptomatic or mild symptoms; clinical or diagnostic observations only; intervention not indicated.
 - Grade 2: Moderate; minimal, local or noninvasive intervention indicated; limiting age-appropriate instrumental activities of daily living (refers to preparing meals, shopping for groceries or clothes, using the telephone, managing money, etc.).
 - Grade 3: Severe or medically significant but not immediately life-threatening; hospitalization or prolongation of hospitalization indicated; disabling; limiting self-care activities of daily living.
 - Grade 4: Life-threatening consequences; urgent intervention indicated.
 - Grade 5: Death related to AE.
- Outcome

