11.1 Adverse Event and Serious Adverse Event Recording and Reporting

All AEs (except non-serious AEs for screening failures) that occur after the signing of informed consent and up to 30 days after last drug administration will be recorded in the eCRF and in the patient’s medical records, whether or not considered by the investigator to be related to the study drug. Thereafter only AEs assessed as related should be recorded. All AEs should be recorded using acceptable diagnoses, if possible. For screening failure patients the non-serious adverse events will not be recorded in the e-CRF but only in the patient’s medical records.

In addition all SAEs will be recorded on the SAE Report Form. Study centres are instructed to report all SAEs and AEs of special interest (ie, infusion-related reactions and allergic reactions to study drug grade 3 or higher, cytokine release syndrome, overdoses) to United Bio Source within 24 hours using the study-specific SAE report form.

Infusion-related reactions and allergic reactions to study drug grade 3 or higher, or cytokine release syndrome, which are AEs of special interest in this study, should be reported along with their respective symptoms (eg, hives, chill, and fever for infusion reaction). Equally, for overdoses the symptoms caused by the overdose should be reported. If an AE has already been reported, it is not necessary to report each individual sign and symptom of that AE as a separate AE. For example, if myocardial infarction is reported as an AE, there is no need to report elevated creatine phosphokinase and abnormal ECG, or other related signs, symptoms, or laboratory values as separate AEs. However, if both occurred in isolation and myocardial infarction was not diagnosed, then each event would be reported as an AE.

All nonserious AEs must be followed up for a final outcome. An outcome of “unknown” is not considered to be an acceptable final outcome. An outcome of “not yet resolved” is an acceptable final outcome for nonserious AEs at the end of a patient’s participation in a study. All SAEs must be followed up for a final outcome until resolution or, if resolution becomes unlikely, until stabilization or death. The follow-up for SAEs that are a progression of NHL only until the end of a patient’s participation in a study is acceptable. This includes obtaining information on recovery and any sequelae and, in case of a fatal outcome, the cause of death.

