11.1 Adverse Events

The primary safety endpoint is the incidence and severity of adverse events (AEs). This endpoint will be determined based on the Safety Population. If not specified otherwise, the adverse events summary and overall table will be displayed overall, by each NHL subtype, and for the combined group of FL and other indolent NHL.

All adverse events (AEs) and serious adverse events (SAEs) will be coded using the Medical Dictionary for Regulatory Activities (MedDRA), Version 20.1.

Treatment emergent AEs are defined as AEs occurring or worsening after the start (date and time) of the first study treatment and up to 30 days after the last study treatment including all treatment cycles (treatment emergent period). However, adverse events occurring or worsening later than 30 days after the last treatment are defined as treatment emergent if these are considered to be related to the study drug.

If the start date and time of an AE are partially or completely missing, the AE will be assumed to be treatment-emergent if it cannot be definitely shown that the AE did not occur or worsen

during the treatment emergent period (worst case approach). Missing dates and times will not be replaced.

Thus, the following approach will be taken:

- If the start time of an AE is missing but the start date is complete, an AE will only be excluded from treatment emergent AEs if start day is before day of first treatment or start day is after end day of treatment emergent period.
- If start time and day are missing but the start month is complete, an AE will only be excluded from treatment emergent AEs if start month is before month of first treatment or start month is after end month of treatment emergent period or if stop date/time is before start of first treatment.
- If start day and months are missing but the start year is complete, an AE will only be excluded from treatment emergent AEs if start year is before year of first treatment or if start year is after end year of treatment emergent period or if stop date/time is before start of first treatment.
- If start date is completely missing, an AE will not be excluded from treatment-emergent AEs unless the stop date/time is before start of first treatment.

Time from first treatment to onset of AE [days] will be calculated for complete dates only and will be included in listings.

An AE summary table will be presented showing the incidence and frequency of any

- Treatment-emergent AEs (TEAEs)

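### For patients who stop before the end of Cycle 2, no scheduled contact secures the 30-day adverse-event window

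*Protocol*

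**What the plan says.** **The window.** Protocol 10.8.1 defines the adverse-event (AE) period: "Temporally associated means after signing the informed consent form until 30 days after last administration of the study drug". Protocol 11.1 requires that all AEs, related or not, "up to 30 days after last drug administration will be recorded in the eCRF"; after that only related events are recorded. SAP 11.1 uses the same limit for treatment-emergent AEs (TEAEs), "up to 30 days after the last study treatment including all treatment cycles (treatment emergent period", and names AE incidence and severity as the primary safety endpoint.

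**The EOS visit for early terminators.** It is timed in three ways:
- Protocol 10.5: "If patient terminates the study early (ie, before end of Cycle 2), the EOS will be performed on the day of termination".
- Protocol 9.11.2, for those who leave before Cycle 2 is finished and response has been read: "should be scheduled for a visit as soon as possible, at which time all of the assessments listed for the End of Study visit should" take place.
- Protocol Table 2, column header: "EOS Visit + 4 weeks ± 2 days", with no exception for early termination.

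For two-cycle completers without at least stable disease, 10.5 says "Patients will have their EOS 4 weeks" (± 2 days) after the last Cycle 2 dose.

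**Other contacts.** Protocol 9.11.2 sets a minimum for everyone who stops study drug: they "will be contacted for safety evaluations during the first 4 weeks following the last dose of study drug". Table 2 footnote 17 adds an evaluation about one month after discontinuation for patients who leave before any response assessment. Section 10.6 makes this a response evaluation, to be done if possible.

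**The concern.** AEs are found mainly because someone asks: Protocol 11 relies on questioning at procedures and appointments, on what patients volunteer, and on assessments. For a patient who terminates early, the EOS visit can coincide with the last dose, and the one remaining safety contact can be made the next day. From then on no planned enquiry would bring out a new event, although the analysis treats the patient as at risk of a TEAE until day 30.

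Such patients stay in the Safety Population, which is everyone dosed. SAP 7.1 analyses withdrawn patients on available data without imputation. An event that nobody elicits is therefore counted as no event, so any error in TEAE, serious AE or death counts is downward. Safety and tolerability is a secondary objective, and the descriptive incidence tables are what the study offers on it.

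**Working it through.** The plan gives no figure for this, so the check is day arithmetic counted from the last dose (day 0).

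**Inputs from the documents**
- AE window: 30 days (Protocol 10.8.1, 11.1; SAP 11.1).
- EOS for early terminators: day of termination (10.5).
- Minimum safety contact: any day in the first 4 weeks, taken as day 1 to day 28 (9.11.2).
- Dosing interval in Cycles 1 and 2: 7 days.
- Discontinuation for persisting drug-related toxicity: after a postponement of more than 15 days (9.6, 9.10), so at least 16 days past the due date.
- Discontinuation on the dosing day is possible, for example after a Grade 4 infusion reaction (9.5.1).

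**Formula:** days left = 30 − day of the last planned safety enquiry. Where both EOS and the contact apply, the later one counts.

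| Route out of treatment | EOS day | Left after EOS | Left after the later of EOS and contact |
|---|---|---|---|
| Stopped on the dosing day | 0 | 30 − 0 = 30 | 30 − 28 = 2 to 30 − 1 = 29 |
| Stopped at the next weekly visit | 7 | 30 − 7 = 23 | 2 to 23 |
| Stopped after more than 15 days' postponement | 7 + 16 = 23 or later | 30 − 23 = 7 or fewer | 2 to 7 if EOS is on day 23 |
| Comparison: two cycles completed without stable disease | 28 ± 2 = 26 to 30 | 0 to 4 | – |

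The contact alone leaves between 30 − 28 = 2 and 30 − 1 = 29 days. Even at its latest it ends 2 days short of the window.

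**Effect of the conflicting EOS rules.** Take a stop on the dosing day, and assume the Table 2 interval runs from that day. A site following the table would see the patient on days 26 to 30, leaving 0 to 4 days. A site following 10.5 would see the patient on day 0, leaving 30. Which passage a site follows thus decides how much of the window a visit covers.

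**The one-month evaluation.** It is counted from discontinuation, so where it takes place it falls near or after day 30. The first planned response assessment is Cycle 2 Day 28, so it applies to this group. It is listed with the imaging rules, is conditional in 10.6, and no AE collection is attached to it.

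**The case against.** **The obligation to day 30 already exists.** This stands. Every dosed patient's AEs must be recorded to day 30, serious events are reportable within 24 hours, and volunteered events count. A reader might infer that the window is not covered at all in early leavers. The documents do not say that; what is missing is a scheduled contact that makes the obligation effective.

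**Known toxicity is followed.** This also stands. Under 9.11.1 an AE that causes withdrawal is monitored to outcome, 10.8 follows any toxicity until it stabilises, returns to baseline or new treatment starts, and 11.1 requires follow-up of AEs and serious AEs. The gap concerns only events that begin after the last contact.

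**The gap is not widest in patients leaving for toxicity.** It is tempting to say that observation is thinnest where toxicity is most likely. The postponement route leaves 7 days or fewer; the infusion-reaction route can leave 30. The documents give no discontinuation rates, and early leavers also include progression and withdrawn consent. That inference is not supported.

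**A percentage-point bias cannot be stated.** Suppose 30% AE incidence over 30 days and a constant hazard. By day 7, 1 − 0.70^(7/30) = 8.0% would have occurred, a shortfall of up to 22 points in early leavers. With 10–20% leaving early, that is up to 2.2–4.4 points overall. All three inputs are assumed. Constant hazard fits poorly with Protocol 4.2.2, where the most frequent AE, infusion reaction (12 of 21, 57.1%), arose entirely at first infusion. A patient who left because of a TEAE is already counted in overall incidence. These figures are ceilings, not estimates.

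**It may be too late to act.** SAP 4.1 expected all patients to have finished main treatment by a July 2015 cutoff, while the protocol version is dated 26 May 2020. This limits the practical effect of a change but does not make the rule sound.

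**Conclusion.** The point holds as a minor weakness in safety ascertainment. For patients who stop before the end of Cycle 2, the plan sets no contact that closes the 30-day AE window, and its passages disagree on when their EOS visit takes place. After EOS, from about 7 days or fewer to all 30 remain, depending on the route out. After the minimum contact, 2 to 29 remain.

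New-onset AEs, serious AEs or deaths in that remainder depend on spontaneous report or on the conditional one-month response evaluation. TEAE incidence may therefore be somewhat too low. The direction follows from the handling of withdrawn patients; the size cannot be derived, because neither discontinuation rates nor AE timing are given. The day counts assume weekly dosing on schedule and sites that do no more than the protocol's minimum. The regular EOS after Cycle 2 shares the problem only to the extent of 0 to 4 days.

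**What to change.** - Keep the EOS assessments at termination. In 9.11.2 and 10.5, time the safety contact that is already required at or just after day 30 from the last dose, for every patient whose EOS falls earlier. Ask about AEs, serious AEs, vital status and new anti-lymphoma therapy. Alternatively, state that AEs are collected at the one-month evaluation where it is done.
- Reconcile 9.11.2, 10.5, 10.6, 11.1, the Table 2 EOS header and footnote 17, so that they give one EOS rule and one AE close-out rule for early terminations.
- If no patient can any longer stop in Cycles 1 or 2, state the limitation in the study report: how many of the Safety Population stopped before the end of Cycle 2, and on which day after the last dose each was last asked about AEs.

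The cost is a sentence or two of protocol text and a telephone call to patients who have left the study. A call will not detect laboratory changes. Keeping the EOS assessments at termination preserves the earlier check within the window.

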10.6 Efficacy

Efficacy will be evaluated in terms of the ORR, SD, DoR, TTP, and PFS. The ORR will be evaluated using the revised IWG criteria (Cheson, 2007) and will be defined as the proportion of patients with CR and PR (CR+PR).

The DoR will be the time from first meeting of criteria for response (ie, CR or PR) to first documentation of relapse or progression.

The TTP is defined as the time from study entry (first dosing) until documented lymphoma progression or death as a result of lymphoma. Deaths from other causes are censored at the time of death.

PFS is defined as the time from study entry (first dosing) until lymphoma progression or death as a result of any cause.

Response criteria are provided in [Section 17.4](#).

CT or PET Examination, or Further Radiological Examinations

CT: For all patients, CT neck/chest/abdomen/pelvis is required as indicated in the schedule of assessments at baseline and at all time points when a radiographic response assessment is performed.

PET: For patients with DLBCL and patients known or expected to have PET-avid lymphomas, a PET scan should be performed at baseline in addition to the CT scan. At the subsequent visits, PET should be done in DLBCL patients or if at baseline the lymphoma was PET-avid, but can be omitted if PET definitely would not change the response assessment according to the clinical judgement of the investigator (eg, CT already shows progressive disease).

MRI may be used in lieu of CT for subjects with contraindications to administration of contrast agents or due to other medical reasons (at the same time windows as CT), or in addition to CT at the discretion of the investigator (in this case, MRI may be performed as/when appropriate). The method used at baseline should be used throughout the study unless otherwise medically indicated.

Additional radiographic evaluations: are to be done, as appropriate. Follow-up radiographic evaluations will be performed for any procedures performed at baseline visit at the end of Cycle 2 and 3 (if applicable) and at the second, fourth and every further follow-up visit. Follow-up radiographic evaluations may be performed anytime \pm 4 days of the planned visit. If

a patient discontinues from the study before any response assessment, if possible a response evaluation will occur approximately one month after the patient discontinues from the study.

CT, PET or additional radiological examinations (eg, MRI) that were done up to 3 weeks before Cycle 1 Day 1 may be used as a patient's baseline assessment at the investigator's discretion.

Physical Examination

The response assessment will be supported by the palpation of lymph nodes from the physical examination (see [Section 10.2](#))

Bone Marrow

At the Screening visit (Baseline), a bone marrow aspirate and a biopsy should be obtained. Results from bone marrow examination done within 4 weeks before screening are acceptable if the patient's disease has been stable since then. In this case only available data will be used and bone marrow examinations at screening for which this data are not available will not be performed. Repeat of marrow aspirates and biopsies should be obtained at Day 28 of Cycles 2 and 3. Histological examination should be performed and the infiltration by malignant B-cells should be evaluated.

If bone marrow has been obtained within 4 weeks before screening and disease has been stable, the bone marrow biopsy does not need to be repeated solely to obtain samples for determination of CD19 expression.

